The proposed Registry is expected to be a valuable and informative risk-management tool within the comprehensive EU Risk Management Plan. It is not intended to provide a quantitative assessment of the benefit-risk of treatment with Nordic Aprotinin. The Registry will address specific issues found in the BART study. In that study it was found that some centres were not applying the appropriate safety measures concerning monitoring of blood coagulation. It was also found that some surgical centres had high morbidity and mortality rates. However there were insufficient data available from the BART study to allow analysis of the contribution of these factors (that is the lack of appropriate risk minimisation measures) to an increased risk of morbidity and mortality. This is why this Registry collects information on the monitoring of blood coagulation.

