9.7. Data analysis

All data analyses will be performed by Dendrite Clinical Systems together with Nordic after the Key Data are completed. Statistical programming and analyses will be performed using SAS and/or other statistical software as required.

Analysed data will be reviewed by an Independent Data Safety Monitoring Committee, involving at least four (4) national coordinating investigators.

The Registry will collect information for all patients who receive Nordic Aprotinin for any purpose in participating countries in Europe. The Registry will not allow a direct comparison of mortality and morbidity among patients treated with aprotinin to patients not with aprotinin. Mortality and morbidity outcomes vary according to patient selection criteria by centre and by country of treatment. Historical controls are not wholly reliable as patient selection and operative techniques vary over time. It is proposed to examine external data bases for comparative purposes as these may be used as a yardstick to measure patient outcomes, e.g. reports from existing national or European cardiac surgical databases. These external data will be mentioned in the Statistical Analysis Plan (SAP) prior to the first analysis.

The analysis of data from the Registry will be descriptive, and all information will be reported in summary tables.

The intention is to focus on those variables most pertinent to assessing compliance with approved labelling, including compliance with the approved indication, and compliance with instructions for appropriate use, including use of heparin and monitoring of anticoagulation. Summary data will be provided for all variables collected and the data will be reported overall, by country, and if required by centre.

The first data analyses will be conducted six months after the completion of data entry of the first subject in the study depending on PSUR scheme and timelines and will be repeated six months later. Thereafter the analyses will be conducted annually until the close of the Registry (i.e. for at least three years). Overall reports will be synchronised between each country so that **the analyses are all conducted at the same time.**

Analysis will be made of the data for Nordic Aprotinin overall, by individual country and if required by individual site. The analysis will include the following key outcomes and variables will be presented:

The outcomes to be included in each report will include at least:

- Death

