- Myocardial infarction (fatal and non-fatal)
- Renal failure (fatal and non-fatal)
- Renal failure with and without aminoglycoside use

- Stroke (fatal and non-fatal)
- Other embolic or thrombotic event (fatal and non-fatal)
- Blood loss: requiring blood product transfusion, requiring re-operation
- Blood product transfusion
- Anaphylaxis

Note: allergic reactions and anaphylactic/anaphylactoid reactions are rare (between 1/10,000 and 1/1,000) and anaphylactic shocks are very rare (below 1/10,000) when appropriate preventative measures are taken so none may be reported. If any occur the details will be reported separately.

Variables included in the analysis:

Analysis of each outcome will be presented by: country, age categories, sex, presence of anti-platelet agents active at time of operation, cardiac by-pass and operative type (on label and off-label). Other variables may be included as considered appropriate by an Independent Data Safety Monitoring Committee or as requested by the PRAC.

The final analysis will be based on the population entered at three years following completion of the first patient. The analysis will include at least the information above and will include further analyses as suggested by the results and as requested by the Competent Authorities concerned and the Independent Data Safety Monitoring Committee (IDSMC).

A review will be conducted by the IDSMC every six months throughout the study. The results of the six months initial interim report and of each annual report will be available in full to the PRAC to allow full review for safety signals. Previous mortality and morbidity data from existing cardiac surgery databases will be available as a yardstick. This may occur when a potential safety signal arises. Outcome data between different participating centres within the Registry may also be analysed when appropriate.

Additional analyses can be made available on a flexible basis depending on the outcomes in the study. In addition to the above further analyses may be undertaken when appropriate according to the ongoing findings from the Registry and as requested by the PRAC (and other Competent Authorities if required).

Rates and confidence intervals:

Rates and exact 95% confidence intervals will be computed for all identified adverse events and potential risks and all relevant criteria.

Missing data:

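### Section 8.1 gives the link from inadequate coagulation monitoring to morbidity and mortality as the reason for collecting monitoring data, but no analysis committed in 8.2, 8.3 or 9.7 compares outcomes by monitoring adherence

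*Protocol*

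**What the plan says.** Section 8.1 of the protocol states: "The Registry will address specific issues found in the BART study". It names two of them. In that trial "some centres were not applying the appropriate safety measures concerning monitoring of blood coagulation", and "It was also found that some surgical centres had high morbidity and mortality rates". It then says there were "insufficient data available from the BART study to allow analysis of the contribution of these factors", which it explains as the lack of risk minimisation measures, to a raised risk of morbidity and mortality. It concludes: "This is why this Registry collects information on the monitoring of blood coagulation".

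The commitments that touch this are:

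- **8.2, primary objective 2:** incidence of death and of thromboembolic events, overall.
- **8.2, primary objective 3:** the proportion of patients monitored as the SmPC recommends, and the proportions below the two ACT thresholds.
- **8.3, secondary objective 1**, under a heading about the contribution of suspected risk factors: among patients with thrombotic events, the proportion not monitored as recommended.
- **9.7, mandatory breakdown of each outcome:** country, age category, sex, active antiplatelet agents, bypass and operative type. Further variables may be added if the monitoring committee or the PRAC wishes.
- **9.7, centre level:** analysis "overall, by individual country and if required by individual site", and "Outcome data between different participating centres within the Registry may also be analysed when appropriate".

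**The concern.** Section 8.1 poses a question about contribution: do patients without adequate coagulation monitoring die or have thrombotic events more often than those with it? That needs outcome rates in both groups. The committed tables give the total event rates, the total monitoring rate, and the monitoring rate among thrombotic cases. None gives an outcome rate by monitoring status, and death is not related to monitoring at all.

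A final report could follow 8.2, 8.3 and 9.7 to the letter and still not address the gap that 8.1 names. The one figure meant to show contribution could also be misread: a high share of unmonitored patients among cases looks like evidence of harm, and may only reflect that monitoring was often not done as recommended.

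**Working it through.** **1. The plan's own figures.** Section 9.5 bases 3,951 patients on a margin of 1.56 points at a proportion of 50%. Check: 1.96² × 0.25 / 0.0156² ≈ 3,946, and the margin at 3,951 is 1.559 points. Inflation for 25% exclusion: 3,951 / 0.75 = 5,268. Both reproduce. They concern one proportion in the pooled registry, so nothing in 9.5 is wrong on this point.

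**2. Aim against commitments.**

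| Needed for the question in 8.1 | Committed? |
|---|---|
| Proportion monitored, all patients | Yes (8.2, objective 3) |
| Proportion not monitored, thrombotic cases | Yes (8.3, objective 1) |
| Proportion not monitored, patients without events | No |
| Thrombotic event rate, monitored and unmonitored | No |
| Death rate, monitored and unmonitored | No |
| Proportion not monitored, deaths | No |

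**3. Why a share among cases is not enough.** Let q be the proportion unmonitored among cases and f the proportion unmonitored among all patients. The crude risk ratio, unmonitored against monitored, is

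RR = q(1 − f) / [f(1 − q)].

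Take q = 30% for illustration. The documents give no value for q or f.

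| f (assumed) | RR |
|---|---|
| 10% | 0.30 × 0.90 / (0.10 × 0.70) = 3.86 |
| 20% | 0.30 × 0.80 / (0.20 × 0.70) = 1.71 |
| 30% | 0.30 × 0.70 / (0.30 × 0.70) = 1.00 |
| 40% | 0.30 × 0.60 / (0.40 × 0.70) = 0.64 |

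The same reported figure fits strong harm, no association and apparent protection.

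**4. Would the missing table be informative?** The documents give neither the unmonitored share nor an event rate, so both are assumed. The power formula for two proportions (normal approximation, two-sided 5%, all 3,951 patients with known status, no allowance for clustering by centre) gives:

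| Unmonitored | Event rate if monitored | Power, RR 1.5 | Power, RR 2.0 |
|---|---|---|---|
| 10% | 3% | 0.39 | 0.82 |
| 10% | 5% | 0.55 | 0.95 |
| 20% | 3% | 0.55 | 0.96 |
| 20% | 5% | 0.76 | >0.99 |
| 30% | 3% | 0.65 | 0.99 |
| 30% | 5% | 0.85 | >0.99 |

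Precision in the 20% case: 0.20 × 3,951 ≈ 790 unmonitored and 3,161 monitored. Exact (Clopper-Pearson) 95% intervals are 4.3% to 5.8% for 158/3,161 (5.0%) and 8.0% to 12.3% for 79/790 (10.0%). Clustering and unknown status would widen them.

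**5. Centre level, if it is used.** The number of centres is not given. For 30, 50, 80 or 120 equal centres (132, 79, 49 or 33 patients each), with the same assumed true death rate of 5% everywhere, the chance that at least one centre shows 10% or more is 0.18, 0.89, >0.99 and >0.99. Case mix acts as well. With assumed death rates of 3% in low-risk and 12% in high-risk patients, a centre with 20% high-risk patients shows 0.8 × 3% + 0.2 × 12% = 4.8%. One with 80% shows 0.2 × 3% + 0.8 × 12% = 10.2%, at equal quality of care.

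**The case against.** The strongest reply is that the study is descriptive by design. Section 8.1 disclaims a quantitative benefit-risk assessment, and 9.5 and 9.7 say the analysis is descriptive. A breakdown by monitoring status is also descriptive, so this does not explain the omission.

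Second, a reader could combine the overall unmonitored proportion from 8.2 with the proportion among cases from 8.3 and back-calculate the crude ratio in step 3. For thrombotic events that is possible in principle, and it limits the point. It yields no planned estimate or interval, it needs both figures to share a denominator (9.7 drops patients lacking the needed information, analysis by analysis), and it cannot be done for death.

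Third, the SAP listed as Annex 6 is not shown and may contain the table. If so, the protocol only needs to say so. As it stands, the protocol's own mandatory list omits it.

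Three stronger readings are tempting, and the documents do not support them:

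- **That 8.1 promises a centre comparison which 9.7 then makes optional.** Section 8.1 mentions centres with high mortality when describing the earlier trial, but what it derives from this is the collection of monitoring data. Sections 4 and 11.2.1 also commit to continuing review for patterns at the level of a country or centre.
- **That 9.7 prescribes crude centre rates.** It does not use the word. Its missing-data paragraph foresees covariate models, and an adjustment method may be in the SAP.
- **That the question goes wholly unanswered.** The thrombotic part has a committed, if weak, patient-level figure.

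**Conclusion.** The mismatch is real but narrower than a failure to compare centres. Section 8.1 justifies the monitoring data by a question on morbidity and mortality. The committed analyses give no outcome by monitoring adherence, nothing linking monitoring to death, and for thrombotic events only a proportion among cases.

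No stated figure is wrong. That a proportion among cases cannot show contribution by itself needs no assumption. The values in step 3 are illustrations, and the power figures rest on assumed event rates of 3% to 5%, unmonitored shares of 10% to 30%, and no clustering. Within that range the registry could describe a doubled risk well (0.82 to >0.99) and a 1.5-fold risk only moderately (0.39 to 0.85).

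The centre figures depend heavily on an unknown number of centres. They support caution if centres are compared, and do not show that a centre comparison is owed.

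**What to change.** In 9.7, add adherence to heparinisation monitoring as recommended in the SmPC (yes, no, unknown) to the variables by which each outcome is presented. Death and thrombotic event rates with exact 95% intervals then appear for each group. The unknown category follows the rule that 9.7 already sets for breakdowns with missing data.

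State that any difference is an unadjusted association. Alternatively, adjust it for Key Data such as age, urgency, procedure and number of previous operations, with allowance for centre.

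If the option in 9.7 to compare outcomes between centres is used, show results with allowance for centre size and Key Data case mix, since 9.7 itself says outcomes vary with patient selection by centre. The particular method can be left to the SAP.

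If none of this is done, narrow 8.1 to say that the registry describes monitoring practice and does not address its contribution to morbidity and mortality.

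The cost is one more breakdown variable. Centre, age, urgency, procedure, previous operations and the heparin and ACT fields are already Key Data (9.3.1, 9.3.2 and 9.3.5), although the minimum ACT is recorded only when available. Residual confounding must be acknowledged in any case, because most pre-operative risk factors are on non-key pages (9.3.9 to 9.3.13) that 9.3 says cannot be completed for all patients.

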----------------------------	---	---	---

	
The Investigator will make all the study-related source data and records available to a quality assurance auditor mandated by the sponsor, or to domestic or foreign regulatory inspectors.
 
The Investigator is required to support audit / inspection activities, to be available to the auditors/inspectors upon request and to permit the auditor/inspector direct access to source data/documents.
	
sponsor, or to domestic or foreign regulatory inspectors.
 
The Investigator is required to support audit / inspection activities, to be available to the auditors/inspectors upon request and to permit the auditor/inspector direct access to source data/documents.
	

9.9 Limitation of the research methods
	
9.9. Limitations of the research methods
 
.....
 
When incomplete data will not be recovered the data manager will try to get the cause (fortuitous omission, not pertinent data due to death or other reason, lack of time...) and a field in the database will be filled by the data manager concerning the cause.
	
9.9. Limitations of the research methods
 
.....
 
When incomplete data will not be recovered the data manager will try to get the cause (fortuitous omission, not pertinent data due to death or other reason, lack of time...) and a field in the database will be filled by the data manager concerning the cause.
	
This sentence was deleted because the NAPaR database do not allow the justification of missing or incomplete data. There is no direct communication between the study datamanager and the participating sites.
 
However, the NAPaR data entry completeness is centrally followed, per country and per site, in order to limit the missing data.
 
For now, the targeted rate of complete key data above 80% has been achieved with the concurrence of Medical Science Liaison (MSL) and/or local coordinator.

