8.2. Primary objectives

The primary objectives of the Registry are to:

1. Monitor the pattern of use and record utilisation information:
 - the proportion of patients exposed to aprotinin in accordance with the authorized indication
2. Measure the incidence of the following adverse events:
 - death and the distribution of the primary cause of death
 - thromboembolic events; the total and individual incidence of myocardial infarction, stroke and other thromboembolic events recorded
 - incidence of renal dysfunction defined as a rise in creatinine from pre-operative to post-operative levels of > 0.5 mg/L, and the incidence of renal dialysis
 - the numbers having an anaphylactic response to aprotinin
3. Measure the effectiveness of risk minimisation measures as described in the RMP and close monitoring of adherence to the SmPC recommendations:
 - the proportion of patients receiving heparinisation monitoring as recommended in the SmPC
 - Proportion of patients with a minimal ACT-celite below 750 seconds
 - Proportion of patients with a minimal ACT-kaolin below 480 seconds
 - the proportion of patients with a post-operative renal dysfunction defined as a rise in creatinine from pre-operative to post-operative levels of > 0.5 mg/L or requiring dialysis known to have received aminoglycoside antibiotics
 - the proportion of patients exposed to aprotinin without the use of test dose (or antibody test)
 - the proportion of patients administered with the recommended posology
 - the proportion of patients administered with less than 2.5 million KIU
 - the proportion of patients administered with more than 7 million KIU

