9.3.5. Intra-operative coagulation and blood loss monitoring in the operating room*

Coagulation prevention details, dose of heparin, either fixed or by titration, before and during surgery;

Monitoring of anti-coagulation, ACT, kaolin or celite;

The minimum operative ACT when available;

The estimated intra-operative blood loss, if available;

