As a matter of fact imputation of data is more or less invention of data that can strongly bias results in an observational study. The less speculative approach is therefore to remove from the data patients without the needed information from the analysis.

In data modelling or if a breakdown of the sample is done according a given variable, a missing data in any qualitative covariate (or factor of segmentation of the sample) can have a category called "unknown". A first model will fitted with such a categorization and a second one will be fitted after removing all patients with missing data on the covariate. If it concerns a breakdown of the sample then descriptive statistics along with 95% confidence interval will be provided for all categories including the unknown class. Regarding quantitative covariate, categorization of the covariate may be done and a first model will be fitted with only categorical variables including the "unknown" category and a

second model is fitted with quantitative covariate (patients with a missing data are excluded). Concerning the breakdown the same categorization approach will be applied and estimation will be provided for each category. If a breakdown of the sample is applied the estimation for the "unknown" category will be compared to all the other categories combined to assess whether missing data represent approximately the average of the collected data.

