The potential limitation induced by missing data due to incompleteness or absence of any data will be assessed through the number of missing data for each variable of key interest and the breakdown by cause of missing information provided by the data manager (see imputation of missing data).

Data are entered in some hospitals by the same person treating the patients, which may increase the risk of social desirability bias (e.g. respondents report what they think is expected to happen, rather than what they actually do). However, in most hospitals, data will be entered by a CRA or a healthcare professional responsible for data entry (under supervision of a physician) or another physician. During visits to cardiac surgery centres and trainings, Nordic (or its representatives) will advise to have different persons treating the patients and entering data. Furthermore, the requested information that needs to be entered into the Registry are factual data, therefore limiting interpretation bias.

The prospective design of the study does not allow evaluating the changes in physicians' behaviour before and after the implementation of the new recommendations. Furthermore, the participation of prescribers as investigators of the study may change their own clinical practice, taking into account that this study will be prospective. This "Hawthorne effect" could bias the results but is common to any clinical trial or registry. As the Hawthorne Effect relates to individual behaviour in response to change, it can be assumed that the healthcare professionals concerned in the Registry are indeed likely to change their behaviour. In fact this is an advantage of the Registry and one reason for it being prospective. **It is important for clinicians to adopt the risk minimisation measures, and the Registry will ensure the risk minimisation measures (and relating results) to be read and implemented multiple times** (i.e. every time a patient is entered in the Registry). Once these measures are adopted they should certainly be a part of the team protocols and so will not disappear when the Registry closes.

Primary objectives are updated to fulfil the current definition of a non-interventional study as per Directive 2001/20/EC Art 2(c). Nordic will promote the prescription of the product in accordance with the terms of the marketing authorisation. Nordic does not plan to evaluate efficacy of off-label use.

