Annex 1. DHPC

15 September 2015

New indication and safety information for aprotinin (Trasylol®), following its re-introduction to the market

Dear Health Care Professional,

Summary

Aprotinin (Trasylol®) will be re-introduced in your country from [date to be confirmed] with a restricted indication and new safety information as follows:

New restricted indication for aprotinin (Trasylol®):

Aprotinin is indicated for prophylactic use to reduce blood loss and blood transfusion in adult patients who are at high risk of major blood loss undergoing isolated cardiopulmonary bypass graft surgery (i.e. coronary artery bypass graft surgery that is not combined with other cardiovascular surgery).

Aprotinin should only be used after careful consideration of the benefits and risks, and the consideration that alternative treatments are available.

New safety information:

The reduced level of heparinisation in the patients treated with aprotinin increases the risk of thrombotic events in this population. The level of heparinisation of patients is incorrectly interpreted with the use of non-appropriate activated clotting tests.

The data illustrates the risks associated with inadequate monitoring of the anticoagulative effect of heparin administered in the CABG procedure.

Aprotinin is not a heparin-sparing agent and it is important that adequate anticoagulation with heparin be maintained during aprotinin-therapy. Elevations in the partial thromboplastin time (PTT) and celite Activated Clotting Time (Celite ACT) are expected in aprotinin-treated patients during surgery, and in the hours after surgery. It is important that adequate anticoagulation with heparin be maintained and monitored during aprotinin treatment. In patients undergoing cardiopulmonary bypass who are being treated with aprotinin, one of the following three methods is recommended to maintain adequate anticoagulation:

- Activated Clotting Time (ACT)
- Fixed Heparin Dose
- Heparin Titration

Partial Thromboplastin Time (PTT) should not be used to maintain adequate anticoagulation with heparin.

An ACT is not a standardized coagulation test, and different formulations of the assay are affected differently by the presence of aprotinin. The test is further influenced by variable dilution effects and the temperature experienced during cardiopulmonary bypass. It has been observed that kaolin-based ACTs are not increased to the same degree by aprotinin as are diatomaceous earth-based (celite) ACTs.

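### Removing patients with a blank adherence endpoint may overstate adherence to the risk-minimisation measures, and the check on missing data in Section 9.9 cannot be produced as written

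*Protocol*

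**What the plan says.** Section 9.7 rejects imputation and fixes the alternative: "The less speculative approach is therefore to remove from the data patients without the needed information from the analysis". It then makes one allowance: "a missing data in any qualitative covariate (or factor of segmentation of the sample) can have a category called 'unknown". That allowance, and the refit with and without the affected patients, concern covariates and breakdown factors. Nothing comparable is given for a blank endpoint.

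Primary objective 3 in Section 8.2 consists largely of adherence endpoints. They include "the proportion of patients receiving heparinisation monitoring as recommended in the SmPC", with ACT sub-items such as "Proportion of patients with a minimal ACT-celite below 750 seconds", the proportion treated without a test dose or antibody test, and the proportion given the recommended posology. Section 9.3.5 collects one of the key inputs conditionally: "The minimum operative ACT when available". The DHPC in Annex 1 accepts ACT, a fixed heparin dose or heparin titration: "one of the following three methods is recommended to maintain adequate anticoagulation".

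Section 9.3 expects some users to return incomplete Key Pages. The only completeness figure is in the Section 5 table of changes, which reports that the target of more than 80% complete Key Data was reached. Section 9.9 plans to judge missingness by counts per key variable and by "the breakdown by cause of missing information provided by the data manager". The reason column of the Section 5 table states that "the NAPaR database do not allow the justification of missing or incomplete data".

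**The concern.** Complete-case removal is unbiased for a proportion only if having a recorded value is unrelated to the value itself. That is hard to take for granted when the endpoint is whether a team followed and documented a safety procedure. Section 8.1 explains that coagulation monitoring is collected because some centres in an earlier trial did not apply the appropriate measures, and Section 9.9 concedes a risk of social desirability bias. If undocumented patients are the less adherent ones, removing them raises every adherence proportion and lowers the proportions that count failures (no test dose, ACT below the limit).

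The ACT items add a second difficulty. A blank minimum ACT may mean that the value was not entered, that no ACT was done, or that another listed method was used. The removal rule treats all three alike.

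At stake is the registry's measure of whether risk minimisation works. A confidence interval computed on the remaining patients would not reveal the error.

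**Working it through.** **The plan's own figures (Section 9.5).** At p = 0.5 and n = 3,951 the 95% half-width is 1.96 × √(0.25/3,951) = 1.559 points, which matches the stated 1.56. Inflating for 25% exclusions gives 3,951/0.75 = 5,268, also as stated. The exclusions listed are refusal, non-exposure and off-pump surgery. Missing endpoint values are not among them.

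**Bias of complete-case removal.** Let m be the share of patients with a blank endpoint, a the adherence among documented patients and q the adherence among removed patients. Then

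- whole-cohort adherence = (1 − m)a + mq
- bias of the complete-case estimate = a − [(1 − m)a + mq] = m(a − q)

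The bias is positive if q < a, zero if q = a and negative if q > a. The bounds come from q = 0 and q = 1.

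**Inputs.** The protocol gives no m for ACT, test dose or posology, and no a or q. I take m = 20% as the ceiling that a completeness above 80% allows for incomplete records, with 10% and 5% beside it. It is not a per-variable rate. The protocol also does not say whether a field collected only when available counts against completeness. The values of a are assumptions.

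| m | a (assumed) | all removed non-adherent | all removed adherent | bias, points |
|---|---|---|---|---|
| 5% | 80% | 76.0% | 81.0% | +4 to −1 |
| 10% | 80% | 72.0% | 82.0% | +8 to −2 |
| 20% | 80% | 64.0% | 84.0% | +16 to −4 |
| 5% | 90% | 85.5% | 90.5% | +4.5 to −0.5 |
| 10% | 90% | 81.0% | 91.0% | +9 to −1 |
| 20% | 90% | 72.0% | 92.0% | +18 to −2 |

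For m = 20% and a = 90%: 0.8 × 0.9 = 72% and 0.8 × 0.9 + 0.2 = 92%. In terms of failures, a documented 10% would be compatible with 8% to 28%.

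**Comparison with the planned precision.** The bias equals 1.56 points when a − q = 1.56/m: 7.8 points at m = 20%, 15.6 at 10% and 31.2 at 5%. With 20% removed, 0.8 × 3,951 ≈ 3,161 patients remain. At a = 90% the half-width is 1.96 × √(0.09/3,161) = 1.05 points, so the interval looks tight whatever q is.

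**The safeguard.** Section 9.9 relies on causes of missingness supplied by the data manager. The Section 5 reason column says the database cannot record them and that the data manager has no direct communication with sites. Section 9.9 also points the reader to imputation of missing data, which Section 9.7 rejects. Counts per variable survive, but no bound is planned from them.

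**The case against.** The strongest reply is that the direction is not established. The bias m(a − q) can be zero or negative, and the illustrative range reaches 92%, above the assumed 90%. This stands, so the finding is conditional.

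Three further objections also stand:

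- A reader might infer that unmonitored patients are deleted. The rule removes only those without the needed information. A recorded absence of monitoring or of a test dose is information, and that patient stays in as non-adherent.
- A reader might treat every blank ACT as a failure. The DHPC lists two methods that do not depend on ACT, and Section 9.3.5 records heparin dose as fixed or titrated.
- A reader might take 18 points as the expected error. It is the extreme case of an assumed adherence and a record-level ceiling spread over seven Key Pages.

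The plan also has real protections: prompts for missing Key Data and continual completeness monitoring (Section 9.6), reconciliation against sales and counts of missing values (Section 9.9). These limit m and make it visible. They say nothing about q.

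It may be said that bounds are detail for the SAP, which is not shown. But the protocol itself fixes removal and confines the unknown class. The mismatch over causes is also more than a difference between a change log and current text: current Section 9.9 promises an output that the sponsor says the database cannot support.

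Extending the point to renal incidence, through deaths before a post-operative creatinine, is not supported to any stated size. Death and dialysis are recorded separately.

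**Conclusion.** The concern holds in conditional form. As written, a blank adherence endpoint drops out of the denominator with no category and no bound, and this may overstate adherence if undocumented patients are less adherent. The size is unknown. Under the assumed m = 20% and a = 90%, the whole-cohort value lies anywhere from 72% to 92%, and modest gaps between documented and undocumented patients would match the planned margin. The documents do not support a claim that adherence is overstated, nor one that it is overstated by any particular amount. The sample-size figures are unaffected. Separately, Section 9.9 does not fit Section 9.7 or the stated limits of the database. This is a cheap improvement to a stated rule that bears on a primary objective.

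**What to change.** - For each proportion under primary objective 3, keep all exposed analysable patients in the denominator with a not-recorded category. Report the complete-case estimate together with the lower bound (all missing non-adherent) and the upper bound (all missing adherent). Do not fix the worst case as the headline, since that is itself a single imputation.
- For heparinisation monitoring, separate patients with no ACT value because another method listed in the DHPC was documented from those with nothing recorded. Reconcile the ACT sub-items in Section 8.2 with the three methods in the DHPC, and give ACT-threshold proportions among ACT-monitored patients, by reagent.
- In Section 9.9, replace the breakdown by cause with missing counts by variable and centre and a comparison of complete and incomplete records. Remove the cross-reference to imputation.

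No new data are needed. The cost is a wording change, one extra column per table and a wider reported range.
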